#### Analysis of all treatment-emergent adverse events

The following TEAE summaries will be generated:

- Overview of TEAEs, summarizing number (%) of patients with:
  - Any TEAE
  - Serious TEAE
  - TEAEs related to study treatment

**Regeneron Pharmaceuticals, Inc.** 

Page 43 of 88

- TEAE leading to death
- TEAE leading to treatment discontinuation
- All TEAEs by primary SOC and PT
- Number (%) of patients experiencing common TEAE(s) presented by primary SOC and PT (PT incidence ≥ 2 patients in any treatment group)

Date: May 16, 2024

- All TEAEs causality relationship (related/not related) to study treatment, presented by SOC and PT
- All TEAEs by maximum severity (ie, mild, moderate, or severe), presented by SOC and PT

#### Analysis of all treatment emergent serious adverse event(s)

• All Serious TEAEs by primary SOC and PT

#### Analysis of all treatment-emergent adverse event(s) leading to treatment discontinuation

• All TEAEs leading to permanent treatment discontinuation, by primary SOC and PT

#### **Patient Deaths**

The following summaries of deaths will be generated.

- Number (%) of patients who died by study period (TEAE) and reason for death
- TEAEs leading to death (death as an outcome on the AE CRF page, as reported by the Investigator) by SOC and PT

#### **5.8.2.** Analysis of Adverse Events of Special Interest

Treatment-emergent adverse events of special interest (AESI), as listed in Section 4.8.1.2, will be presented by SOC and PT as applicable. AESI are defined by SMQ, CMQ, lab data, and/or dedicated e-CRF are summarized by frequency (%) as described in Appendix 10.3.

#### **5.8.3.** Adverse Events of Interest

Treatment emergent adverse events for mild infusion reactions, mild hypersensitivity reactions, and injection site reactions (ISR) as defined in Section 4.8.1.3 will be summarized by patient frequency (%) by SOC and PT.

Treatment emergent adverse events for infusion reactions and hypersensitivity reactions will also be summarized regardless of severity by SOC and PT.

#### **5.8.4.** Clinical Laboratory Measurements

General clinical laboratory parameter actual values (quantitative) and change from baseline values will be descriptively summarized at baseline and each post-baseline visit (collected up to the day of last dose of study treatment + 14 days). These parameters will be presented by the biological functions defined in Section 4.8.2.

Individual patient laboratory parameter measurements will be additionally evaluated by PCSV criteria (See Appendix 10.4), specifically identifying patients with at least one post-baseline

Regeneron Pharmaceuticals, Inc.

Page 44 of 88

measurement that meets the PCSV criteria within the respective TEAE period. These laboratory parameters will be presented by the biological functions defined in Section 4.8.2. The incidence of PCSVs at any time during the respective TEAE period will be summarized regardless of the baseline level, and again according to the following baseline categories:

- Normal (according to PCSV criterion/criteria)/missing
- Abnormal according to PCSV criterion or criteria

Patient listings of laboratory measurements that meet PCSV criteria will be provided for the report appendix. For those laboratory parameters that don't have an associated PCSV criteria, similar summary tables can be provided based on measurements outside the central laboratory normal ranges, if applicable.

#### 5.8.5. Analysis of Vital Signs

The vital sign actual values and change from baseline values obtained will be descriptively summarized at baseline and each post-baseline visit, collected up until the day of the last dose of study treatment + 14 days.

Individual patient vital sign measurements (regardless of sitting position) will be additionally evaluated by PCSV criteria, specifically identifying patients with at least one post-baseline measurement that meets the PCSV criteria within the TEAE period. The incidence of PCSVs at any time during the respective TEAE period will be summarized regardless of the baseline level, and again according to the following baseline categories:

- Normal (according to PCSV criterion/criteria)/missing
- Abnormal according to PCSV criterion or criteria

Patient listings of vital sign measurements that meet PCSV criteria will be provided for the report appendix.

#### 5.8.6. Analysis of 12-Lead ECG

ECG results will be presented through an overall interpretation of ECG status and by ECG parameters (HR, PR, QRS, QT and QTcF), collected up until the day of the last dose of study treatment + 14 days.

- ECG parameters will be summarized through an overall interpretation of ECG status, specifically normal or abnormal (includes clinically significant (Yes/No)). The count and percentage of patients with at least 1 abnormal post-baseline ECG during the respective TEAE period will also be summarized according to the following baseline status categories:
  - Normal/missing
- Abnormal
  - Individual patient ECG measurements will be additionally evaluated by PCSV criteria, specifically identifying patients with at least one post-baseline measurement that meets the PCSV criteria within the TEAE period. The incidence of PCSVs at any time during the respective TEAE period will be

Regeneron Pharmaceuticals, Inc.

Page 45 of 88

Protocol: R4461-PLD-20100

summarized regardless of the baseline level, and again according to the following baseline categories:

Protocol: R4461-PLD-20100

Date: May 16, 2024

- Normal (according to PCSV criterion/criteria)/missing
- Abnormal according to PCSV criterion or criteria
  - Patient listings of ECG measurements that meet PCSV criteria will be provided for the report appendix.

#### 5.8.7. Physical Exams

A list of patients with any clinically significant abnormality results will be generated.

#### **5.8.8.** Treatment Exposure and Treatment Compliance

The duration of exposure during each study part in weeks will be presented by treatment group and study period, calculated as:

(Date of last study drug injection in the specific study part – date of first study drug injection in the specific study part + 7 days)/7

Number (%) of patients exposed to study drug during the study will be presented for each treatment group and study period.

In addition, duration of exposure during the study will be summarized for each treatment group using number of patients, means, SD, minimums, medians, and maximums.

A summary of the number of doses by treatment group and study period will be provided.

The compliance with study treatment will be calculated as follows:

Compliance % = 100% 
$$\times \frac{\text{\# actual injections}}{\text{\# planned injections}}$$

The treatment compliance will be presented by specific ranges for each treatment group and study period.

### 5.9. Analysis of Other Variables

All measurements, scheduled or unscheduled, will be assigned to the Analysis Windows (Appendix 10.2) in order to provide an assessment for all post-baseline visit.

Change from baseline liver volume and hepatic fat content by MRI will be descriptively summarized by treatment group (Arm 1, Arm 2) and cohort (Cohort A, Cohort B, and combined Cohort A+B) at weeks 12 and 24 for patient in the MRI analysis set. Mean difference between treatments with associated 95% CI will also be provided at week 12.

Change from baseline in body composition (including lean mass and fat mass) using DXA at weeks 12 and 24 will be descriptively summarized by treatment group (Arm 1, Arm 2) and cohort (Cohort A, Cohort B, combined Cohort A+B) in patients in FAS and have at least one post-baseline assessment.

Regeneron Pharmaceuticals, Inc.

Page 46 of 88

5.11.

Change from baseline in leptin level at weeks 12 and 24, will be descriptively summarized by treatment group (Arm 1, Arm 2) and cohort (Cohort A, Cohort B, combined Cohort A+B) in patients in FAS and have at least one post-baseline assessment.

Summary statistics will include the number of patients with data, mean, SD, median, minimum, maximum, Q1 and Q3.

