The percent change in hepatic fat (assessed by magnetic resonance imaging-derived proton density fat fraction [MRI-PDFF]) is a key secondary endpoint and the analysis is structured to understand whether there are different responses by cohort. There is 1 published study of the effects of metreleptin on hepatic steatosis in FPLD patients (Simha, 2012). It reported a baseline mean liver hepatic fat of 13.8% with a standard deviation (SD) of 6.1% in 24 patients with FPLD. In this open-label observational study, a 43% reduction in percent hepatic fat (SD of 27%, coefficient of variation of 63%) was reported after 3 months of metreleptin treatment. It is anticipated that REGN4461 will improve hepatic steatosis, similar to what has been observed with metreleptin therapy (Javor, 2005) (Oral, 2002) (Petersen, 2002) (Brown, 2018a) (Brown, 2018b).

While HbA1c provides an excellent estimate of average glucose levels, it does not provide information on insulin sensitivity. Non-invasive measurements of insulin sensitivity will be used including the Homeostatic Model Assessment of Insulin Resistance (HOMA-IR), which incorporates measures of fasting insulin and glucose. Also 2 additional surrogate measurements of insulin sensitivity will be analyzed. First is the Lipoprotein Insulin Resistance Index (LIPO-IR) which incorporates the amount and size distribution of lipoproteins to estimate insulin sensitivity given the known changes in lipoprotein profiles that occur across a wide range of insulin sensitivity (Shalaurova, 2014). The final surrogate of insulin sensitivity is the Adipose Insulin Resistance (ADIPO-IR), which incorporates fasting serum insulin and free fatty acid (FFA) levels.

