#### 1.2.4. Modifications from the Statistical Section in the Final Protocol

The content of this SAP reflects the content of the statistical section of Protocol R4461-PLD-20100 Amendment 1 with the following exceptions:

- Protocol Section 4. Endpoints: The definitions of endpoints are clarified in SAP Section 5.7 by replacing:
  - "elevated baseline fasting TG" into "screening TG"
  - "elevated baseline HbA1c" for defining subgroup into "screening HbA1c" to match HbA1c strata (screening HbA1c ≤7.0%, >7.0%)
  - "baseline leptin" for defining Cohort into "screening leptin"
- Protocol Section 11.3.2. Safety Analysis Set: Safety analysis set (SAF) is replaced with DB SAF and SB SAF as follows in SAP Section 3.2:
  - DB SAF includes all randomized patients who received any double-blind study drug.
  - SB SAF includes all the patients in the double-blind SAF who also received at least 1 study drug in the single-blind treatment period.
- Protocol Section 11.4.5.4. Treatment Compliance: Compliance % calculation is replaced with study treatment administration interval compliance in SAP Section 5.8.8.
- Protocol Section 11.4.3. Efficacy Analyses: The randomization strata per IVRS in the analysis models (eg, MMRM) are replaced with actual strata in SAP Section 5.7 to reflect the actual disease characteristic for statistical modeling.
- Protocol Section 11.4.3. Efficacy Analyses: Due to the early termination of the study and subsequent limited number of participants enrolled, only descriptive summaries

Protocol: R4461-PLD-20100

and line plots for fasting TG, HbA1c, fasting glucose, liver fat (MRI-PDFF), and Daily Lipodystrophy Hunger Questionnaire (DLHQ) over time will be provided by treatment group. Spaghetti plots for fasting TG, HbA1c, fasting glucose, liver fat (MRI-PDFF), and DLHQ will be provided for individual patient data across visits for the endpoints by treatment group if applicable.

Protocol: R4461-PLD-20100

Date: May 16, 2024

• SAP Section 7 Timing of Statistical Analyses: First Step Analysis and Second Step Analysis will not be performed.

# 1.2.5. Revision History for Statistical Analysis Plan Version 1

This is the original version of the SAP.

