## **Sensitivity Analysis**

- A non-parametric approach will be performed on the primary efficacy endpoint for comparing the mibavademab and placebo. Specifically, the percent change in fasting serum TG from baseline to week 12 will be ranked for an analysis of covariance (ranked ANCOVA). For the case >5% missing data at week 12, missing data will be imputed using multiple imputation based on other observed measurements. The ranked ANCOVA model will be able to provide significance of the treatment effect as compared to placebo. Nominal p-values will be provided as a measure of the strength of evidence. Median treatment difference and its 95% confidence interval can be derived from the Hodges-Lehmann estimation and Moses distribution free confidence interval respectively.
- To assess the impact of a systemic dosing error on the primary efficacy endpoint, the primary efficacy analysis will be performed excluding affected patients. Patients known to be under dosed at the time of database lock will be identified for this analysis before database lock. Any additional patients determined to be affected post-database lock will be separately identified.

## 5.7.1.2. Change in HbA1c from Baseline to Week 12

Absolute change from baseline to week 12 in HbA1c, will be analyzed in the FAS population for the Cohort A patients using a mixed-effect model with repeated measures (MMRM) approach. The MMRM model will include the following effects: fixed categorical treatment groups (Placebo, mibavademab), time points (weeks 4, 6, 10, and 12), actual strata (screening HbA1c ≤7.0%, >7.0%), strata-by-time-point interaction, and treatment-group-by-time-point interaction, as well as the continuous fixed covariates of baseline HbA1c value and baseline value-by-time point interaction. An unstructured covariance matrix will be used to model the within patient errors. In the case that the unstructured covariance matrix does not converge, then a structured covariance matrix such as autoregressive heterogeneous [ARH] will be assessed.

Post-baseline data available up to and including the week 12 efficacy analysis window for HbA1c (Table 12 in Appendix 10.2) will be used and missing data are accounted for by the MMRM. Contrast and estimate statements will be used to assess baseline adjusted least-squares

Regeneron Pharmaceuticals, Inc.

Page 35 of 88

Protocol: R4461-PLD-20100

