#### 5.7.2.1. Continuous Endpoints Anticipated to have a Normal Distribution

Continuous secondary variables defined in Section 4.7.2 and Section 4.7.3 anticipated to have a normal distribution (including HbA1c, fasting glucose, and liver fat) will be analyzed using a similar MMRM model as described for the primary endpoint in HbA1c.

Daily lipodystrophy hunger questionnaire (DLHQ) will be descriptively summarized from baseline to week 12 and again from baseline to week 24. Mean changes in monthly averaged DLHQ scores (±SE) will be plotted across visits by treatment group; a spaghetti plot will be provided for individual patient data across visits by treatment group. Monthly averaging windows of the DLHQ scores are defined in the Efficacy Analysis Windows for Daily Lipodystrophy Questionnaire (See Appendix 10.2). If a participant reported less than 10 scores

Protocol: R4461-PLD-20100

within a monthly averaging window for a DLHQ item, the averaged score will be assigned a missing value.

The statistical estimates, comparisons, and descriptive statistics for these secondary efficacy variables are summarized in Table 3, Table 4, Table 5, and Table 6.

Table 3. Summary of Statistical Estimates and Comparisons in Normally-distributed Secondary Endpoints

Endpoint	Cohort for Modeling	Analysis Method / Estimates	Comparisons
• Absolute change in HbA1c from baseline to week 12.	• Separately for Cohort B and Cohort A+B	MMRM / Least-squares (LS) means with their corresponding standard errors and 95% confidence intervals.  Note: Strata level = HbA1c>7.0%.  Note: Post baseline visits to include in the model are weeks 4, 6, 10, and 12.	REGN4461 versus Placebo with nominal p- value.
• Change in fasting glucose from baseline to week 12.	• Separately for Cohort A, Cohort B, and Cohort A+B	MMRM / Least-squares (LS) means with their corresponding standard errors and 95% confidence intervals.  Note: Strata level = HbA1c>7.0%.  Note: Post baseline visits to include in the model are weeks 2, 4, 6, 8, 10, 11, and 12.	REGN4461 versus Placebo with nominal p- value.
• Percent change in liver fat (MRI-PDFF) from baseline to week 12	• Separately for Cohort A, Cohort B, and Cohort A+B	MMRM / Least-squares (LS) means with their corresponding standard errors and 95% confidence intervals.  Note: patient subgroup = baseline MRI-PDFF ≥8.5%  Note: Post baseline visit at week 12.	REGN4461 versus Placebo with nominal p- value.

Protocol: R4461-PLD-20100

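### The week-12 between-arm MRI difference in SAP 5.9 subtracts the baseline scan but does not adjust for it, and the A+B contrast has no leptin-cohort term

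*SAP*

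**What the plan says.** SAP 5.9 (Analysis of Other Variables) states: "Change from baseline liver volume and hepatic fat content by MRI will be descriptively summarized by treatment group", and by cohort (A, B and A+B), at weeks 12 and 24. It then adds: "Mean difference between treatments with associated 95% CI will also be provided at week 12". It names no model, baseline term, HbA1c stratum or leptin cohort.

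Elsewhere the SAP says so when it intends adjustment. In 5.7.2.1, liver fat "will be analyzed using a similar MMRM model as described for the primary endpoint in HbA1c". That model (5.7.1.2) includes the actual HbA1c strata and "the continuous fixed covariates of baseline HbA1c value and baseline value-by-time point interaction". Table 3 applies it to percent change in MRI-PDFF at week 12 in patients with baseline MRI-PDFF of at least 8.5%, giving LS means, 95% CIs and a nominal p-value. With week 12 as the only post-baseline visit, this amounts to an ANCOVA.

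SAP 1.2.4 then withdraws modelling: "Due to the early termination of the study and subsequent limited number of participants enrolled, only descriptive summaries" and plots will be given for a list of variables. The list includes MRI-PDFF but not liver volume. Liver volume has no adjusted analysis anywhere in the visible text.

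Protocol 8.6 stratifies randomisation by screening HbA1c within each leptin cohort. Protocol 6.1 collects two baseline MRI assessments during the run-in.

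**The concern.** A difference in mean change treats the slope of the week-12 value on baseline as exactly 1. When the true slope is lower, an arm that starts higher by chance tends to fall further whatever its treatment, and the contrast absorbs that. With about 10 patients per arm in a cohort, chance imbalance is not small. If the treated arm starts higher, the estimated reduction is exaggerated; if it starts lower, the reduction is understated.

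The pooled A+B contrast has a second gap. Allocation was separate within cohort, so cohort belongs in the comparison. Leaving it out puts any between-cohort difference in mean change into the error term.

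At stake are the reading and precision of one descriptive estimate. For liver volume it is the only between-arm estimate visible in the plan. For hepatic fat it may be the only one left, depending on how far SAP 1.2.4 reaches.

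**Working it through.** **The plan's own precision figures.** SAP Table 2 gives none for MRI outcomes. Its 90% half-widths for the co-primaries reproduce as t(0.95, 2n−2) × SD × √(2/n):

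- HbA1c, SD 1.81: 1.72 (n=7), 1.59 (n=8) and 1.40 (n=10), against 1.72, 1.59 and 1.4.
- Log TG, SD 0.87, n=10: 0.67, against 0.67.

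**Inputs for hepatic fat.**

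- Protocol 3.2.1, on a published metreleptin study: "It reported a baseline mean liver hepatic fat of 13.8% with a standard deviation (SD) of 6.1% in 24 patients with FPLD". So SD = 6.1 points.
- The same section reports a 43% reduction at 3 months, uncontrolled. As a rough yardstick, 0.43 × 13.8 = 5.9 points.
- Planned size (Protocol 7.1): 20 per cohort, 1:1, so 10 per arm per cohort and 20 per arm for A+B.
- Assumed: rho, which the documents do not give; equal SD at both visits; and n = 5 per arm to represent truncated enrolment.
- No SD is given for liver volume, so it cannot be sized.

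**Imbalance carried by the change score.** The SE of the baseline difference is 6.1 × √(2/n). With equal SDs, the contrast carries −(1 − rho) of it.

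| n per arm | SE of baseline difference | Shift per 1 SE, rho 0.5 | Shift per 1 SE, rho 0.8 |
|---|---|---|---|
| 5 | 3.9 | 1.9 | 0.8 |
| 10 | 2.7 | 1.4 | 0.5 |
| 20 | 1.9 | 1.0 | 0.4 |

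At 10 per arm, 1.4 and 0.5 points are about 23% and 9% of the 5.9-point yardstick (1.36/5.93 and 0.55/5.93). If week-12 spread is smaller than at baseline, the slope falls below rho and the share carried rises.

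**Interval width.** The change-score variance is 2(1 − rho)SD², and the baseline-adjusted variance is (1 − rho²)SD², a ratio of (1 + rho)/2. Allowing for lost degrees of freedom and chance covariate imbalance, the width ratio is √[(1 + rho)/2 × (1 + 1/(2n−4))] × t(0.975, 2n−3)/t(0.975, 2n−2).

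Worked at n=10, rho 0.5:

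- Unadjusted: 2.101 × 6.1 × √(2/10) = 5.73 points.
- Adjusted: 2.110 × 6.1 × √0.75 × √(2/10) × √(1 + 1/16) = 5.14 points.
- Ratio: 0.90.

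Adjusted/unadjusted 95% CI width, baseline as the only covariate:

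| n per arm | rho 0.5 | rho 0.7 | rho 0.8 | rho 0.9 |
|---|---|---|---|---|
| 5 | 0.96 | 1.02 | 1.05 | 1.08 |
| 10 | 0.90 | 0.95 | 0.98 | 1.01 |
| 20 | 0.88 | 0.94 | 0.96 | 0.99 |

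Break-even is near rho 0.87 at 10 per arm and 0.63 at 5 per arm.

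**Simulation check** (3,000 runs per cell; stratum balanced and given no prognostic effect). Adding one stratum term to baseline gives 0.90, 0.96, 0.99 and 1.01 at n=10, and 0.99, 1.06, 1.09 and 1.12 at n=5, for the same four rho values. Coverage was about 95% for adjusted and unadjusted intervals alike.

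The gain from a cohort term in A+B depends on how far mean change differs between cohorts. The documents do not give this, so it is not sized.

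**The case against.** The best opposing case has four parts.

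- **The premises pull apart.** SAP 1.2.4 makes 5.9 matter for liver fat because enrolment stopped early, yet 10 per arm is the full planned size. If enrolment were full, the adjusted model in Table 3 would cover liver fat. Ten is also a ceiling, since Protocol 9.2.2.11 limits MRI-PDFF to capable sites and exempts patients with contraindications. This stands, and it is why the fix depends on sample size. It does not help liver volume, which has no adjusted analysis at any size.
- **Adjustment can hurt.** At 5 per arm and rho 0.7 the adjusted interval is about 2% wider with baseline alone and 6% wider with a stratum term. This stands too. Smaller samples, however, also mean larger chance imbalance.
- **The output is descriptive.** Protocol 11.1 plans no formal testing and 5.9 gives no p-value, so power is not the yardstick. Agreed; the argument rests on width and imbalance only.
- **The inputs are thin.** Rho and equal SDs are assumed, and liver volume cannot be sized. Agreed.

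A reader might also infer more than the documents support:

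- *That the baseline scan is ignored.* It is not: the outcome is change from baseline, so the scan is subtracted. It is only not a covariate.
- *That the interval is wrong.* Its coverage is nominal, and the estimate is unbiased over repeated randomisation. The imbalance problem is conditional on the trial in hand.
- *That 5.9 is certainly the surviving liver-fat contrast.* SAP 1.2.4 amends Protocol 11.4.3 and is not confined to SAP 5.7, so it may limit the hepatic-fat contrast in 5.9 as well. The text does not settle this.

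**Conclusion.** The point holds as a modest one. SAP 5.9 gives a 95% CI for a between-arm difference without naming the estimator. The natural reading is an unadjusted difference in mean change, with no cohort term for A+B. That estimate is valid but less protected than it could be against a chance baseline difference, and at planned size it is somewhat less precise at low to moderate rho. The benefit of adjusting fades as rho approaches 0.9 and can reverse in very small samples.

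The sizes rest on an SD of 6.1 points from one cited study, the same spread at both visits, and assumed correlations. Actual numbers scanned are not in the documents, and the MRI analysis set named in 5.9 is not defined in SAP Section 3. Parts of Protocol 4.3 and SAP 4.9 are blank in the public copy, so the statement about liver volume covers the visible text only.

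**What to change.** In SAP 5.9, name the estimator:

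- For liver volume and hepatic fat, report an ANCOVA of week-12 change on treatment and baseline value, with the LS mean difference and its 95% CI. Add leptin cohort for A+B. Add the HbA1c stratum only if numbers allow.
- Where a cohort has only about 5 or fewer scanned patients per arm, keep the unadjusted difference, label it descriptive, and show baseline means by arm beside it.
- Reconcile 1.2.4, 5.7.2.1 with Table 3, and 5.9, so that it is clear which liver-fat contrast will be reported.

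The cost is a few sentences and one model call, with no new data. The downside is one to three degrees of freedom, which can slightly widen the interval when the sample is very small or rho is high.
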